Signature

Date

Abstract

Title	Gallium-68 Prostate Specific Membrane Antigen (68Ga-PSMA) PET for Imaging of Thyroid Cancer: A Feasibility Study
Patient population	
The study population will consist of patients with thyroid cancer.
 
Key Eligibility Criteria:
 
 • History of thyroid cancer. • Whole body ¹⁸F-FDG PET, I-123 or I-131 scintigraphy within the past 360 days demonstrating uptake • Age 18 years or older at the time of study entry
Rationale for Study	Agents targeting prostate specific membrane antigen (PSMA) are under investigation for both imaging and therapy of prostate cancer. However, despite its name, PSMA expression is not specific to prostate, and is seen in a variety of normal tissues and cancers. In particular, recent case reports have demonstrated that ⁶⁸ Ga-PSMA ligands demonstrate uptake in thyroid cancer. Intriguingly, a recent case report of a patient with thyroid cancer demonstrated a greater sensitivity for metastatic lesions using ⁶⁸ Ga-PSMA as compared to ¹⁸ F-FDG. This suggests the potential use of PSMA PET as a diagnostic (and, in radioiodine-negative thyroid cancers, therapeutic) agent in patients with thyroid cancer.
Primary Objective	
 • To determine the feasibility and utility of ⁶⁸Ga-PSMA PET imaging in patients with thyroid cancer
Secondary Objectives	
 1. To assess the correlation between targeted molecular uptake of ⁶⁸Ga-PSMA-11 in thyroid cancer compared to areas identified as tumor by radioiodine uptake (in well-differentiated cancers) or ¹⁸F-FDG uptake (in poorly differentiated and/or radioiodine-negative cancers). 2. To determine and compare the sensitivity and specificity of ⁶⁸Ga-PSMA-11 PET to ¹⁸F-FDG PET and/or radioiodine scintigraphy
Exploratory Objectives	
 1. To determine if ⁶⁸Ga-PSMA PET uptake is related to tumor differentiation and PSMA staining in tissue pathology when available 2. To determine the correlation between SUV_{max} of target thyroid cancer lesions on ⁶⁸Ga-PSMA PET and serum thyroglobulin levels.
Study Design	This is a single center pilot study investigating the use of ⁶⁸ Ga-PSMA PET in patients with thyroid cancer.
Number of patients	40 patients will be accrued over an approximate 24-month period. It is estimated that all patients will have routine diagnostic imaging, and all patients will have elevated serum thyroglobulin.

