2.2 Secondary

1. To assess the correlation between targeted molecular uptake of ⁶⁸Ga-PSMA PET in thyroid cancer compared to areas identified as tumor by radioiodine uptake (in well-differentiated cancers) or ¹⁸F-FDG uptake (in poorly differentiated and/or radioiodine-negative cancers).
2. To determine and compare the sensitivity and specificity of ⁶⁸Ga-PSMA PET to ¹⁸F-FDG PET and/or radioiodine scintigraphy

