2.3 Exploratory Objectives, Other Assessments

1. To determine if ⁶⁸Ga-PSMA PET uptake is related to tumor differentiation and PSMA staining in tissue pathology when available
2. To determine the correlation between SUV_{max} of target thyroid cancer lesions on ⁶⁸Ga-PSMA PET and serum thyroglobulin levels.

3 Study Design

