3.3.1 Inclusion Criteria

1. History of thyroid cancer
2. Whole body ^{18}F -FDG PET/CT, I-123 or I-131 scintigraphy within the past 360 days of the scheduled ^{68}Ga -PSMA PET demonstrating uptake.
3. Age 18 years or older at the time of study entry
4. Creatinine $\leq 3.0 \text{ mg/dL}$
5. Ability to understand a written informed consent document, and the willingness to sign it

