5.1.1 Screening Assessments

The Screening procedures and assessments must be completed within 28 days of the Day 1 Visit, unless otherwise noted.

A written, signed, informed consent form (ICF) and a Health Insurance Portability and Accountability Act (HIPAA) authorization must be obtained before any study-specific assessments are initiated. A copy of the signed ICF will be given to the subject and a copy will be filed in the medical record. The original will be kept on file with the study records.

All patients who are consented will be registered in OnCore®, the UCSF Helen Diller Family Comprehensive Cancer Center Clinical Trial Management System (CTMS). The system is password protected and meets HIPAA requirements.

In addition to OnCore, REDCap will be used to collect data for this study. REDCap is a secure, HIPAA-compliant, web-based system.

- Complete medical history
- Baseline standard staging diagnostic exams may be done approximately 360 days before PSMA PET as clinically indicated. Patients may receive staging scans and ⁶⁸Ga-PSMA PET imaging on the same day if the patient meets eligibility criteria for the study as assessed by the Principal Investigator prior to the completion of the scan.
- Pregnancy testing in women of childbearing potential (WOCBP)
- Creatinine
- Thyroglobulin

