6.10 Analyses Plans

The number of ^{68}Ga PSMA-11 PET-positive lesions and number of overall thyroid cancer lesions detected by standard staging scans will be descriptively reported for each patient and correlated with the lesions observed in standard MRI imaging. In addition, the mean, range, and standard deviation of SUV_{max} (across all visualized lesions per patient) and $SUV_{max-avg}$ (across all patients in the study cohort) will be descriptively reported.

For each lesion detected on ^{18}F -FDG PET or radioiodine scintigraphy (^{131}I), the presence or absence of ^{68}Ga -PSMA-11 uptake will be reviewed and tabulated. Presence on either ^{131}I and ^{18}F -FDG will be considered true positive disease. If additional lesions are detected on ^{68}Ga -PSMA-11 as compared to ^{18}F -FDG or ^{131}I , the lesions will be characterized as either true or false positives in comparison to the appearance of the lesion on conventional imaging (thyroid ultrasound, CT and MRI). The gold standard for an individual lesion will be FDG or ^{131}I , if the individual lesion is positive on either imaging study. If the lesions are not seen on either FDG or ^{131}I , then consensus reading of conventional imaging will be performed to determine true and

false positive lesions. The total number of lesions detected using each technique will be compared, and this data will be used to determine the sensitivity and specificity of ^{68}Ga -PSMA-11 for the detection of disease. If a larger number of lesions are detected using ^{68}Ga -PSMA-11 compared to ^{18}F -FDG PET and ^{131}I , this provides promising preliminary data, which can be used to justify study in a larger clinical trial.

The patient cohort will be dichotomized by thyroglobulin level. The mean $\text{SUV}_{\text{max-avg}}$ between dichotomized subgroups will be compared using the non-parametric Mann-Whitney U test. The correlation between SUV_{max} on ^{68}Ga -PSMA PET and thyroglobulin level as a continuous variable will also be determined using Pearson correlation method.

In those patients with adequate archival FFPE the correlation between SUV_{max} on ^{68}Ga -PSMA PET and tumor PSMA expression will be explored using Pearson correlation method.

7 Study Management

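### The thyroglobulin analyses use the whole cohort, but no entry criterion ensures that every patient's tumour makes thyroglobulin; any that do not fall in the low group and can hide, inflate or create the association

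*Combined protocol and SAP*

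**What the plan says.** The abstract's entry on the number of patients gives, as an estimate, that "all patients will have elevated serum thyroglobulin".

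The disease criterion in section 3.3.1 is "History of thyroid cancer". It is joined by an imaging criterion: uptake on FDG PET/CT or on I-123 or I-131 "scintigraphy within the past 360 days of the scheduled" PSMA scan. The other criteria are age, creatinine and consent. Neither 3.3.1 nor the exclusion list in 3.3.2 mentions histology or a Tg level. Section 5.1.1 lists "Thyroglobulin" among the screening assessments, with no qualifying value. Section 2.2 expects FDG to be the reference "in poorly differentiated and/or radioiodine-negative cancers".

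Exploratory objective 2 (section 2.3) is the correlation between lesion SUVmax on PSMA "PET and serum thyroglobulin levels". For it, section 6.10 states: "The patient cohort will be dichotomized by thyroglobulin level". The patient-average SUVmax "between dichotomized subgroups will be compared using the non-parametric Mann-Whitney U test". A Pearson correlation with Tg as a continuous variable follows. The section gives no cut-off, no restriction by histology and no rule for undetectable values.

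**The concern.** Serum Tg can stand for tumour only where the tumour makes it. It is general subject knowledge, not stated in the documents, that medullary cancer does not. FDG uptake alone satisfies the imaging criterion, so such a patient can be enrolled. The plan also has this histology in view, since section 1.1 cites a guideline on medullary carcinoma.

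Under 6.10 as written, this patient's Tg is treated as a low value on the same scale as everyone else's. In a cohort of 40, a few such patients sit together in the low group, and their PSMA uptake then helps decide the result. At stake is whether exploratory objective 2 can be interpreted. A reader of the results could not tell a relation between PSMA uptake and Tg from a difference in uptake between histologies.

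**Working it through.** **Figures in the plan.** No effect size, alpha, power or cut-off is given for the Tg objective, so there is no planned figure to reproduce for it. The only sample-size figure is in section 6.8: power 0.87 with 20 patients per comparison, sensitivity 0.65 against 0.90, one-sided 0.05. It reproduces as an exact one-sample binomial test that rejects at 17 or more of 20: P(X ≥ 17 | 0.65) = 0.044 and P(X ≥ 17 | 0.90) = 0.867. It does not bear on this point.

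**Is elevated Tg secured?**
- Entry (3.3.1): any thyroid cancer, with uptake on at least one of FDG, I-123 or I-131.
- Exclusion (3.3.2): nothing on histology or Tg.
- Screening (5.1.1): Tg measured, but no value admits or excludes.
- Analysis (6.10): whole cohort.

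The expectation of elevated Tg is therefore not enforced at any step, and 6.10 does not set aside patients in whom it fails.

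**Illustration on the planned tests.** From the plan: n = 40, Mann-Whitney on two Tg groups, Pearson on continuous Tg. Assumed, because the documents are silent:
- correlation of 0.5 between SUV and log10 Tg in producing tumours, with log10 Tg of mean 2 and SD 1;
- non-producers fixed at log10 Tg = −1, that is (2 − (−1))/1 = 3 SD below the mean, with SUV independent of Tg;
- a median split, and two-sided 0.05;
- 4 or 8 non-producers (10% or 20% of 40).

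With no non-producers, Mann-Whitney power is about 0.71. Otherwise:

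| SUV of non-producers | 4 of 40 | 8 of 40 |
|---|---|---|
| same as the rest | 0.59 | 0.48 |
| 1 SD higher | 0.33 | 0.06 |
| 1 SD lower | 0.80 | 0.87 |
| after restriction to producers | 0.65 | 0.62 |

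These are simulated values; separate runs agree to within about 0.02.

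**Splitting the loss at equal SUV.** With 4 non-producers, power falls by 0.71 − 0.59 = 0.12. Restriction recovers 0.65 − 0.59 = 0.06; the other 0.71 − 0.65 = 0.06 is the cost of fewer informative patients and cannot be recovered. With 8, the fall is 0.71 − 0.48 = 0.23, of which 0.62 − 0.48 = 0.14 is recovered.

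**No true relation.** With a true correlation of 0 and non-producers 1 SD lower in SUV, Mann-Whitney gives p < 0.05 in about 8% (10% non-producers) or 18% (20%) of trials, against a nominal 5%. Restriction returns this to about 4 to 5%.

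**Pearson on untransformed Tg.** At equal SUV, the share with p < 0.05 is 0.46 with 4 non-producers included and 0.47 without them; with 8 it is 0.40 and 0.42. Restriction therefore changes little there. If their SUV is 1 SD higher, the share with 4 included drops to about 0.31.

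**The case against.** The strongest reply is that the number of non-producers may be zero. The population the plan evidently has in mind is follicular-derived: well-differentiated, poorly differentiated or radioiodine-negative disease (2.2), and patients with raised Tg and a negative iodine scan (1.1). The abstract's sentence is a planning estimate, and nothing in 6.10 depends on it. The objective is exploratory, in a 40-patient pilot, with no decision attached. All of this stands and limits the weight of the point. It does not remove the point, because 6.10 has no rule for such a patient if one is enrolled.

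A reader might infer three stronger things that the documents do not support.

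- **That a history of thyroid cancer alone admits a patient.** Recent FDG or radioiodine uptake is also required. FDG uptake does not, however, imply raised Tg.
- **That non-producers must mask the relation.** The direction depends on their PSMA uptake, which the documents do not give. With lower uptake the association is strengthened or created. Figures from a rank or log-scale correlation would also overstate the loss for untransformed Pearson, which is what 6.10 describes.
- **That the analysis must be stratified by TSH state,** because radioiodine and FDG patients differ in stimulation. The documents never mention TSH, so the premise comes from outside them, and stratifying about 40 patients would cost precision.

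**Conclusion.** The point holds in limited form. The estimate that all patients have elevated Tg is not secured by entry, and 6.10 as written would class any non-producing tumour as low Tg. The possible effect on the Mann-Whitney comparison is not negligible. With 4 non-producers, power ranges from 0.33 to 0.80 according to their SUV, against about 0.65 after restriction; with 8, it ranges from 0.06 to 0.87 against about 0.62. Untransformed Pearson hardly changes at equal SUV.

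These sizes rest on an assumed correlation of 0.5, a median split, Tg near the assay floor in non-producers, and an assumed number of them. They show what could happen, not what will. Only exploratory objective 2 is affected; the primary objective, the sensitivity comparison and the sample size are not. This is a cheap improvement.

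**What to change.** In section 6.10, limit the Mann-Whitney and Pearson Tg analyses to patients with follicular-derived cancer. Name the histologies that count, so that borderline types are assigned before SUV is seen. Report SUVmax and Tg for all other patients, and for any without a histology on record, in a descriptive listing. Exploratory objective 1 already needs tumour differentiation, so the histology comes from existing reports.

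In the abstract, delete the sentence on elevated Tg or limit it to the patients in whom Tg is informative. TSH at the Tg draw may be noted descriptively where it is on file, but should not be used to stratify.

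Eligibility, procedures and the total of 40 stay as they are. The cost is a few sentences, one data field drawn from existing records, and a slightly smaller analysed set for one exploratory objective.

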1.1 Background on Indication

Thyroid cancer is the most common endocrine malignancy, with approximately 62,000 new cases per year in the United States (1). The vast majority of thyroid cancers respond favorably to initial therapy with surgical resection and in some cases radioiodine ablation or external beam radiotherapy or a combination of these therapies. However, a subset of patients with aggressive and less differentiated thyroid cancer refractory to radioiodine therapy ultimately succumb to their illness, with approximately 2,000 deaths per year in the US (2). For patients with disease that is refractory to surgical management or radioiodine ablation, treatment options include external beam radiation and kinase inhibitors. Options for restaging of these patients with thyroglobulin elevation but negative iodine scintigraphy (TENIS syndrome) include ¹⁸F-FDG PET/CT and conventional anatomic imaging with ultrasound, CT, or MRI. Nevertheless, the prognosis for these patients remains poor. Therefore, there is an unmet clinical need for therapies to help slow the progression of disease in patients with aggressive forms of thyroid cancer.

1.2 Rationale for the Proposed Study

Agents targeting prostate specific membrane antigen (PSMA) are under investigation for both imaging and therapy of prostate cancer (3,4). However, despite its name, PSMA expression is not specific to prostate, and is seen in a variety of normal tissues and cancers (5,6). In particular, recent case reports have demonstrated that ⁶⁸Ga-PSMA ligands demonstrate uptake in thyroid cancer (7-10). Intriguingly, a recent case report of a patient with thyroid cancer demonstrated a greater sensitivity for metastatic lesions using ⁶⁸Ga-PSMA as compared to ¹⁸F-FDG (7). This suggests the potential use of ⁶⁸Ga-PSMA PET as a diagnostic (and, in radioiodine-negative thyroid cancers, therapeutic) agent in patients with aggressive forms of thyroid cancer.

2 Objectives of the Study

2.1 Primary

- To determine the feasibility and utility of ⁶⁸Ga-PSMA PET imaging in patients with thyroid cancer

2.2 Secondary

1. To assess the correlation between targeted molecular uptake of ⁶⁸Ga-PSMA PET in thyroid cancer compared to areas identified as tumor by radioiodine uptake (in well-differentiated cancers) or ¹⁸F-FDG uptake (in poorly differentiated and/or radioiodine-negative cancers).
2. To determine and compare the sensitivity and specificity of ⁶⁸Ga-PSMA PET to ¹⁸F-FDG PET and/or radioiodine scintigraphy

2.3 Exploratory Objectives, Other Assessments

1. To determine if ⁶⁸Ga-PSMA PET uptake is related to tumor differentiation and PSMA staining in tissue pathology when available
2. To determine the correlation between SUV_{max} of target thyroid cancer lesions on ⁶⁸Ga-PSMA PET and serum thyroglobulin levels.

3 Study Design

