5.1.4 Optional repeat scan

An optional follow up ^{68}Ga -PSMA PET study may be obtained between 2 and 6 months after completion of the first PET. Optional PET will be performed to determine any interval changes in PSMA uptake and compare them to clinical changes including thyroglobulin. The potential for follow-up examination will be discussed and consented for during the original consent process. The study team will contact the patient after completion of the PET about repeat imaging. Sections 5.1.2 and 5.1.3 will be followed during the follow-up imaging.

A maximum number of two ^{68}Ga -PSMA studies (initial and optional follow up) will be performed under this protocol.

Period/ Procedure	Screening	Imaging	Optional Imaging
Study Day/Visit Day	-28 to 1	D1	2-6 months after 1st ⁶⁸Ga- PSMA PET
Informed consent	X		
AE assessment			X ²
Concomitant medications	X	X	X ²
Clinical procedures			
Medical history including prior/concomitant systemic therapies for thyroid cancer	X		
Laboratory procedures			
Creatinine	X		
Thyroglobulin	X		
Pregnancy test (HCG) (WOCBP only)	X		
Imaging procedures			
Standard diagnostic scans as clinically indicated ¹	X ¹		
⁶⁸ Ga-PSMA-11 administration		X	X ²
Whole body PET/MRI		X	X ²

1. Standard of care PET scan may be done up to 360 days before PSMA PET. Patients may receive staging scans and 68Ga-PSMA PET imaging on the same day if the patient meets eligibility criteria for the study as assessed by the Principal Investigator prior to the completion of the scan.
2. Only required if patient agrees to optional follow-up 68Ga-PSMA PET.

6 Reporting and Documentation of Results

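### The thyroglobulin analyses pool values that cannot be reliably separated by TSH state, anti-thyroglobulin antibody or residual thyroid tissue, so the correlation with PSMA uptake may be weakened or inflated

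*Combined protocol and SAP*

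**What the plan says.** Section 2.3 sets as its second exploratory objective the correlation of target-lesion SUVmax on 68Ga-PSMA "PET and serum thyroglobulin levels".

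The laboratory tests in section 5.1.1 and in the schedule after section 5.1.4 are creatinine, thyroglobulin and a pregnancy test. Thyroglobulin is scheduled once, at screening: "The Screening procedures and assessments must be completed within 28 days of the Day 1 Visit, unless otherwise noted". TSH and anti-thyroglobulin antibody do not appear in the screening list, the schedule, the eligibility criteria or the analysis plan.

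Section 3.3.1 requires a history of thyroid cancer and an FDG, I-123 or I-131 study showing uptake within 360 days. It sets no thyroidectomy, TSH, antibody or thyroglobulin criterion. The abstract expects raised thyroglobulin in every patient, but this is not an entry rule.

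On background data, section 5.1.1 lists "Complete medical history". The schedule words this as "Medical history including prior/concomitant systemic therapies for thyroid cancer" and has a separate row, "Concomitant medications", ticked at screening and at imaging.

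Section 6.10 states: "The patient cohort will be dichotomized by thyroglobulin level". SUVmax-avg is then compared between the two groups by Mann-Whitney. The correlation between SUVmax on 68Ga-PSMA "PET and thyroglobulin level as a continuous variable will also be determined using Pearson correlation method". No cut-point, transformation, covariate, stratum or exclusion is given.

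**The concern.** The premise is general clinical chemistry and is not in the documents: measured thyroglobulin depends on more than tumour. It rises when TSH is raised, interfering antibodies can make an assay read low, and residual thyroid tissue secretes it.

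The plan allows all three conditions into one dataset. Section 6.8 assumes that half the patients are imaged with I-131. Section 5.1.1 lets staging scans fall on the same day as the PSMA scan, and thyroglobulin may be drawn at any time in the 28 days before. A value drawn around radioiodine preparation can therefore sit beside one drawn under TSH suppression. Entry does not require thyroidectomy.

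What is at stake is how objective 2 can be read. A weak correlation would not show that uptake is unrelated to tumour thyroglobulin. A strong one could partly reflect the conditions under which the samples were drawn. For TSH and antibody, values from the same sample may not be recoverable later.

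**Working it through.** **The plan's own figure.** The only design figure is power 0.87 with 20 patients per comparison, sensitivity 0.90 against 0.65, one-sided 0.05 (section 6.8). An exact one-sample binomial test that succeeds at 17 or more of 20 has alpha P(X ≥ 17 | 0.65) = 0.044 and power P(X ≥ 17 | 0.90) = 0.867, so the figure reproduces. It concerns the sensitivity comparison and has no bearing on this point. No figure is given for the thyroglobulin analyses.

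**Inputs.** From the documents: n = 40 and a Pearson correlation. Everything else is assumed: true r = 0.5 between SUVmax and log thyroglobulin, SD of log10 thyroglobulin 0.7 to 1.0, a two-sided 0.05 test, and the shares and fold changes below.

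**Clean values.** Power = Φ(atanh(r)·√(n−3) − 1.96) = Φ(0.549 × 6.083 − 1.96) = 0.92. At n = 40, 80% power needs r of about 0.43.

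**Disturbance unrelated to uptake.** Let a share f be stimulated k-fold and a share a be antibody-lowered d-fold. The added variance is v = f(1−f)(log10 k)² + a(1−a)(log10 d)², and the observed r is 0.5 × SD/√(SD² + v).
- f = 0.3, k = 5, a = 0.1, d = 10: v = 0.21 × 0.489 + 0.09 × 1 = 0.193. At SD 0.7, r = 0.42 and power 0.79; at SD 1.0, r = 0.46 and power 0.85.
- f = 0.5, k = 10, a = 0.2, d = 10: v = 0.25 + 0.16 = 0.41. r = 0.37 to 0.42, power 0.65 to 0.78.
- As the second, but d = 100: v = 0.25 + 0.16 × 4 = 0.89. r = 0.30 to 0.36, power 0.46 to 0.64.

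Simulation of the same settings (6,000 trials each) agrees to within about 0.02. Taken together, r is about 0.29 to 0.46 and power 0.46 to 0.86. With a median split, 12 to 16% of patients land in the wrong half in the first setting and 20 to 26% in the second.

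**Disturbance related to uptake.** Section 2.2 ties radioiodine to well-differentiated and FDG to poorly differentiated or radioiodine-negative cancers, and exploratory objective 1 asks whether uptake follows differentiation. TSH state may therefore go with uptake. Take 20% stimulated tenfold, SD 1.5 on the natural-log scale, and uptake shifted by c SD in that group:
- covariance = 0.5 × 1.5 + c × 2.303 × 0.16 = 0.75 + 0.368c
- variance of uptake = 1 + 0.16c²
- variance of log thyroglobulin = 2.25 + 5.302 × 0.16 = 3.098
- c = 0: r = 0.75/√3.098 = 0.43
- c = +1: r = 1.118/√(1.16 × 3.098) = 0.59
- c = −1: r = 0.382/√(1.16 × 3.098) = 0.20

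In a simulated mix of 50% stimulated, 20% antibody-lowered and 10% with thyroid in situ, c = −1 gives about −0.05, which is essentially no correlation.

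**Scale.** Section 6.10 states no log transform. If thyroglobulin is roughly log-normal, simulation with perfectly clean values on the untransformed scale gives a mean r of only about 0.31 to 0.36 and power of about 0.50 to 0.65, against 0.92 on the log scale.

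**Restricting the analysis.** Removing 10 to 20% for antibodies leaves 36 to 32 patients. With r = 0.5 and one covariate, power = Φ(0.549 × √(n−4) − 1.96) = 0.87 to 0.83. Removing a further 20% for thyroid in situ leaves about 29 to 26, and power is 0.78 to 0.73.

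**The case against.** The strongest reply is that the plan collects more than its laboratory list suggests. A complete medical history would ordinarily hold thyroid surgery, concomitant medications could show thyroid hormone or a TSH-stimulating drug, and the type and date of the qualifying scan are known. This stands in part. A reader might infer that thyroid status goes unrecorded and that nothing allows the values to be separated, but the documents do not support that. They show only that thyroidectomy or remnant status is not a named field and is not used in the analysis. None of these sources gives a TSH value or an antibody result.

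A reader might also infer that the correlation must be diluted. That follows only if the disturbance is unrelated to uptake, which the documents give no reason to assume.

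The size rests on nothing in the plan. Staging scans may be up to 360 days old, thyroglobulin must be drawn within 28 days, and the schedule's same-day footnote opens with the standard-of-care PET scan, so stimulated sampling may be uncommon. If the abstract's expectation of raised thyroglobulin in every patient is met, it limits antibody-lowered values, though it does not separate stimulated from suppressed ones. All of this stands.

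Finally, this is the second of two exploratory objectives in a 40-patient pilot and has no power target. That stands too, and it sets the priority.

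**Conclusion.** The point holds as a limit on interpretation. Thyroglobulin is the only thyroid laboratory test, and every value enters one split and one Pearson correlation. Values affected by TSH state, antibodies or residual thyroid tissue cannot be reliably separated.

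Neither the number of patients affected nor the direction of the error can be established from the documents. The ranges above are illustrations that rest on an assumed true r, SD, prevalences and fold changes. The missing log transform may cost as much as the pooling or more: in the mildest setting above, pooling lowers log-scale power from 0.92 to about 0.79 to 0.86, while clean values on the raw scale already give only about 0.50 to 0.65.

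A reader might also infer that restricting the main analysis to patients with interpretable values costs no power. The figures do not show this. Once patients without thyroidectomy are also excluded, power may be near 0.73 to 0.78, so the restriction belongs in a sensitivity analysis.

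This is a cheap improvement to an exploratory objective, of low priority. The primary objective, the sensitivity comparison and the sample size are unaffected.

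**What to change.** - **Section 5.1.1 and the schedule:** record TSH and anti-thyroglobulin antibody with the thyroglobulin sample, using the chart value where it was reported with that sample and otherwise adding the tests to the same tube. Make thyroidectomy/remnant status a named field in the medical history.
- **Section 6.10, main analysis:** keep all patients, but use log thyroglobulin for the Pearson correlation, or use Spearman.
- **Section 6.10, sensitivity analysis:** prespecify both thyroglobulin analyses in antibody-negative, post-thyroidectomy patients, adjusted for or stratified by TSH status. List the remaining patients separately.

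The cost is two assay values, one history field and some wording. The restricted analysis has fewer patients and possibly lower power, so it should support the all-patient result and not replace it. The data items need to be added before enrolment or as early in it as possible.
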